Eltrombopag for post transplant thrombocytopenia
2009-0106

Core Protocol Information

Study Chairman:	[name]
Department:	Stem Cell Transplantation and Cellular Therapy
[contact]
Unit:	423
Full Title:	Eltrombopag for post transplant thrombocytopenia
Protocol Phase:	Phase II
Version Status:	Terminated 04/16/2018
Version:	20
Document Status:	Final

Abstract

Objectives:

Primary Objective

- 1.1 To compare the efficacy of eltrombopag and placebo as defined by proportion of patients achieving platelet count $\geq 30 \times 10^9/l$ by day 57 in patients with thrombocytopenia post hematopoietic cell transplantation (HCT).

Secondary Objectives

- 1.2 To describe and estimate toxicity graded as per National Cancer Institute (NCI) criteria.
- 1.3 To estimate clinical benefit as defined by:
 - 1.3.1 Proportion of patients achieving platelet count $\geq 50 \times 10^9/l$ by day 57
 - 1.3.2 Number of platelet and red cell transfusions
 - 1.3.3 Bleeding as determined by NCI criteria
- 1.4 To determine the optimum dose of eltrombopag in this patient population.
- 1.5 To estimate pre and post treatment thrombopoietin levels and correlate these with platelet response.
- 1.6 To measure drug level and correlate it with response.

Rationale: (Be as concise as possible)

Low platelet count, which is usual after HCT, significantly increases the risk of bleeding. The incidence of bleeding post HCT is 34%, which is moderate or severe in 23% of the patients. Currently regular platelet transfusion remains the mainstay of therapy, with most patients requiring platelet transfusion several times a week. This imposes a significant burden on transfusion services and increases the cost.

Reduced platelet production is a major cause of thrombocytopenia post transplant with increased platelet destruction playing a minor role. Platelet recovery occurs between 11 – 28 days post transplant. Delayed platelet recovery (primary thrombocytopenia) occurs in 5%-25% of patients 8 weeks after HCT. Furthermore, 20% of patients develop secondary thrombocytopenia, defined as a drop in platelet count not due to disease relapse after an initial platelet recovery. Secondary thrombocytopenia is caused by both impaired production and increased destruction resulting from dysregulated immune system. It is often associated with Graft versus host disease and drugs like ganciclovir.

Thrombopoietin (TPO) is the primary regulator of platelet production, and is required for proliferation and differentiation of its precursors. Eltrombopag is a nonpeptide small molecule that stimulates thrombopoiesis by activating TPO receptor.

Eltrombopag received approval from the FDA for the treatment of chronic Idiopathic Thrombocytopenic Purpura (ITP). In a randomized placebo controlled trial in patients with ITP, 59% eltrombopag patients and 16% placebo patients responded achieving a platelet count $\geq 50,000$ per μL with an odds ratio of 9.61 (95% CI 3.31-27.86; $p < 0.0001$). It also increases platelet counts in patients with thrombocytopenia and cirrhosis due to hepatitis C.

In light of its significant efficacy in increasing platelet production and modest toxicity, It is certainly a promising agent for patients who develop thrombocytopenia post stem cell transplantation.

Eligibility: (List All Criteria)

Inclusion:

- 1) Patients ≥ 35 days post HCT with Platelet count $\leq 20 \times 10^9/\text{l}$ sustained for 7 days or patients are platelet transfusion dependent, and
- 2) Neutrophil count $\geq 1.5 \times 10^9/\text{l}$ anytime within the last seven days before enrollment. Patients can be on myeloid or erythroid growth factors for example filgrastim), and
- 3) Age ≥ 18

Exclusion:

- 1) Recurrence or progression of primary malignancy after HCT
- 2) ALT ≥ 2.5 times the ULN

- 3) Serum bilirubin >2mg/dl (unless due to Gilbert's syndrome)
- 4) Documented deep vein thrombosis within 1 year before enrollment on the study, except if upper arm thrombosis related to central venous catheters, within 3 months before enrollment on the study.
- 5) ECOG Performance status >2
- 6) Pregnancy: Women of child-bearing potential and men must agree to use contraception prior to study entry and for the duration of study participation. A woman of child-bearing potential is defined as a woman who has not been naturally post-menopausal for at least 12 consecutive months or with no previous surgical sterilization. A negative pregnancy test result will be required before any study drug is given.

Is there an age limit? Yes

Why? Provide scientific justification:

It is a new molecule that has not been previously tested in children.

Disease Group:

Blood And Marrow Transplantation

Treatment Agents/Devices/Interventions:

Eltrombopag

Proposed Treatment/Study Plan:

Dosage and Administration

Eltrombopag will be given as a single daily dose orally on an empty stomach (1 hour before or 2 hours after a meal). Starting dose will be 50 mg. Dose will be modified as detailed below. Eltrombopag or placebo will be continued for 8 weeks. East Asians will start at 25mg daily.

Allow at least a 4-hour interval between eltrombopag and other medications (e.g., antacids), calcium-rich foods (e.g., dairy products and calcium fortified juices), or supplements containing polyvalent cations such as iron, calcium, aluminum, magnesium, selenium, and zinc.

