5.1 Monitoring and Dose adjustment

5.1.1 Patients in the treatment group will be started at dose level 0 (table 1), the dose will be modified every 2 weeks based on the schema outlined in table 2 after a careful review of safety information at the previous dose level.

Table 1 Dose Level

Dose level	Eltrombopag dose

-1	25mg
0	50mg
1	75mg
2	125mg
3	150mg

Table 2 Dose Modification Schema

Platelet count X 10 ⁹ /l	Dose
< 50	Increase by 1 dose level
50-200	No change
201-400	Decrease by 1 dose level
> 400 at any time	Stop the drug

- 5.1.2 Drug will be stopped and patients will be taken off study if at any time platelet count is $\geq 400 \times 10^9/l$. This count will be carried forward to day 57 for analysis of primary endpoint and counted as success.
- 5.1.3 Patients of East Asian ancestry will start at dose level -1 and dose escalation will stop at dose level 2 (maximum dose 125 mgs).
- 5.1.4 The study drug will be stopped after 8 weeks and all patients will be monitored for additional 4 weeks after the last dose of study drug.
- 5.1.5 Patients will be taken off study: 1) at patient request, or 2) after completing 12 weeks.

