5.2 Evaluations During Study

Table 3 Monitoring

	Pre Study (within 3 days of consent)	Week 1-12 (every 2 wks)###	Post Completion of study drug**
CBC, Na, K, Cl, CO ₂ , ALT, Bili, Alk Phos, albumin, tot protein, BUN & creatinine	X	X	X
PT/PTT	X		X
Thrombopoietin	X		X
PK Studies		X^^	
Toxicity assessment (history and PE) (Graded per NCI toxicity criteria)	X	X	X
Bone Marrow (incl reticulin and collagen staining)	X#		X^
B-HCG pregnancy test in women of child- bearing age	X##		
No. of Platelet & RBC transfusions	X (in the 4 wks prior to study entry)	X	X
Immune Reconstitucional Studies ***	X		X
Ophthalmic Evaluation	X ⁺		X ⁺⁺

A previous biopsy done within one year is acceptable for baseline purposes and a separate bone marrow biopsy will not be required. To assess for fibrosis, special staining for reticulin and collagen will be performed.

Negative pregnancy test is required prior to receiving drug but is not required prior to consent.

Visits at Week 10 and 12 will done by telephone interview and blood work can be drawn locally.

^ First routine bone marrow done after study completion for assessment of disease status will be stained for reticulin and collagen to assess fibrosis. The bone marrow will be performed within 3 months after the last dose of study drug.

^^ No PK studies will be drawn for weeks 10 and 12.

** Date of last dose of study drug.

+ Within 6 months of study entry.

** Within 3 months of last dose of study drug. This will be done earlier if patients develop visual symptoms indicative of cataract.

*** Peripheral blood T-cell subsets, NK and B-cell immune reconstitution

Note: All assessments to be done within 3 days of stated time point.

Statistical Considerations:

Overview

This will be a randomized, double-blind Phase II trial to compare eltrombopag and placebo in patients with thrombocytopenia post transplant. The primary endpoint will be development of a platelet count $\geq 30 \times 10^9/l$ by day 57 without platelet transfusion.

Adaptive Randomization

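### Objective 1.4 promises an optimum dose, but dose is never randomized: within the eltrombopag arm it follows each patient's own platelet counts

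*Combined protocol and SAP*

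**What the plan says.** Two secondary objectives concern dose and exposure: "1.4 To determine the optimum dose of eltrombopag in this patient population" and "1.6 To measure drug level and correlate it with response".

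The Overview and Adaptive Randomization text under Statistical Considerations describes two arms, eltrombopag and placebo. Dose is not a randomized factor.

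Dose within the eltrombopag arm is set as follows:

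- **Start.** 50 mg (level 0), except that "East Asians will start at 25mg daily". Section 5.1.3 repeats this and adds a ceiling: "Patients of East Asian ancestry will start at dose level -1 and dose escalation will stop at dose level 2".
- **Changes.** Under 5.1.1, "the dose will be modified every 2 weeks based on the schema outlined in table 2", and this happens "after a careful review of safety information at the previous dose level". In Table 2 a count below 50 means "Increase by 1 dose level", 50-200 means no change, and 201-400 means one level down.
- **Stops.** Section 5.1.2 takes patients with very high counts off drug and counts them as successes. Safety Monitoring stops the drug for attributed toxicity of grade 3 or higher, with restart at the investigator's discretion.

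For drug levels, the PK row of Table 3 is marked in the two-weekly column, with the footnote "No PK studies will be drawn for weeks 10 and 12". On an 8-week course this points to draws at weeks 2, 4, 6 and 8.

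The supplied text gives no criterion for an optimum dose, and objective 1.6 does not say which level or which measure of response is meant. The Analysis Methods entry refers the reader to a fuller protocol that is not part of the material.

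**The concern.** To determine an optimum dose is to claim what different doses would do in comparable patients. Here patients at different doses are not comparable, because the titration rule sorts them by how their platelets have behaved. Patients with persistently low counts move up. Those at 50-200 stay, and those with very high counts stop and are scored as successes at whatever dose they had reached. Escalation is tied to 50 and the primary endpoint to 30, so a transfusion-free patient at 30-49 is a responder on the primary definition and still goes up a level.

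A table of response by dose reached would therefore mix the effect of dose with the reasons for being at that dose. An optimum-dose statement drawn from it could mislead later dose selection.

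Drug levels drawn after a dose change carry the same feedback, in part, into objective 1.6.

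**Working it through.** The plan gives no sample size, power or precision for either objective, so there is no stated figure to reproduce. The check follows the titration rule.

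**1. Dose paths.** Inputs: Table 1 (levels -1 to 3 are 25, 50, 75, 125 and 150 mg), Table 2, 5.1.3, and 8 weeks of treatment. Two-weekly changes that can affect dosing fall at weeks 2, 4 and 6.

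| Counts at weeks 2, 4, 6 | Weeks 1-2 | 3-4 | 5-6 | 7-8 |
|---|---|---|---|---|
| 50 mg start, always <50 | 50 | 75 | 125 | 150 |
| 50 mg start, always 50-200 | 50 | 50 | 50 | 50 |
| 25 mg start, always <50 | 25 | 50 | 75 | 125 |
| 25 mg start, always 50-200 | 25 | 25 | 25 | 25 |

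From level 0, level 3 needs three upward moves (0 + 1 + 1 + 1). So 150 mg requires counts below 50 at all three reviews and can be taken for about 8 - 6 = 2 weeks. From level -1, three moves give level 2, so 125 mg is the most that can be reached, also for about 2 weeks. The safety review and toxicity stops can delay or prevent an increase but cannot add one, so these are upper limits.

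**2. Direction of the bias.** Take a deliberately simple model with no dose effect. The rates are assumed, not from the documents. All patients start below 30. In each 2-week period the chance of rising is 0.10, with no fall-back. At each review 5% leave before the dose change, keeping their last dose and count; leavers below 30 count as failures. Two recovery patterns are compared.

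*(a) Rises go one band at a time (<30, then 30-49, then ≥50).* Nobody is at ≥50 by week 2, so everyone who stays goes up, and only week-2 leavers have 50 mg as last dose. Their response rate is 0.10. For 150 mg, the shares still below 50 at week 6 are 0.9³ = 0.729 (<30) and 0.081 + 0.162 = 0.243 (30-49). Response at week 8 is (0.0729 + 0.243)/(0.729 + 0.243) = 0.3159/0.972 = 0.325. The 150 mg group looks 22.5 points **better**.

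*(b) Half of first rises go straight from <30 to ≥50.* Last dose 50 mg now holds week-2 leavers (0.05, response 0.10) and stayers already at ≥50 (0.95 × 0.05 = 0.0475, all responders): (0.005 + 0.0475)/0.0975 = 0.538. For 150 mg the week-6 shares are 0.729 and 0.0405 + 0.081 = 0.1215, giving (0.0729 + 0.1215)/0.8505 = 0.1944/0.8505 = 0.229. The 150 mg group looks 31 points **worse**.

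Dose does nothing in either case; only the recovery pattern differs, and the sign reverses. In (a) with no leavers, no one ends on 50 mg and the contrast does not exist. These figures show that the sign is undetermined. They are not estimates for this trial.

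**3. Size of the arm.** If all 64 patients are enrolled, the first 20 at 1:1 give 10 on eltrombopag and the other 44, at 20% to 80%, give 8.8 to 35.2. The expected arm is about 19 to 45. For a correlation on a continuous scale (two-sided 5%, 80% power), the detectable value is tanh(2.80/√(n-3)): tanh(2.80/√16) = 0.60 at n = 19 and tanh(2.80/√42) = 0.41 at n = 45.

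**The case against.** The strongest reply is that the supplied text is an abstract and sends the analysis methods elsewhere. A criterion for optimum, a longitudinal dose-response model or a named PK time point may exist in the full protocol. Nothing supplied says that response will be tabulated by dose reached or correlated with the last level. This stands, and it makes the bias conditional on such an analysis. It does not rescue the wording of 1.4, since no analysis section can create a randomized dose comparison in a two-arm trial. A model using the count history could estimate a dose slope, but that slope would depend on the model's assumptions about recovery.

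It can also be said that both objectives are secondary. That is correct and limits the weight of the point.

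Three stronger readings are tempting and are not supported:

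- *That high doses will look worse by a predictable amount.* The working shows that the sign can go either way.
- *That few patients would reach 150 mg, because only one of the 27 up/same/down sequences leads there.* The sequences are not equally likely. Patients enter with counts of 20 or less or transfusion dependent, and any count below 50 moves them up.
- *That objective 1.6 is invalid, or that week 2 gives the only usable level.* A patient at 50-200 at week 2 has no change, so the week-4 sample is also untouched by titration. A week-2 level avoids titration feedback but not ordinary confounding, for example a shared cause of low exposure and poor recovery. A longitudinal exposure model is equally defensible.

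**Conclusion.** The point holds for objective 1.4. The design cannot determine an optimum dose, because dose is not randomized and is driven by the patient's own platelet counts from a fixed or ancestry-based start. A comparison by dose reached is confounded. Its bias has no fixed size or sign, since both depend on recovery pattern and dropout, and no point gap should be quoted. What follows from the documents alone is that 150 mg is open only to patients below 50 at weeks 2, 4 and 6, for about 2 of 8 weeks. This assumes that reviews fall at weeks 2, 4 and 6 and that Table 2 is applied as written.

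For objective 1.6 the point is a secondary suggestion, conditional on the full protocol not already fixing the level and the analysis.

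A reader might infer that the efficacy result is compromised. It is not: the primary comparison, the adaptive randomization and the death/relapse monitoring rule do not use dose reached or drug level.

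**What to change.** Leave the dosing rules as they are.

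1. **Objective 1.4.** Restate it as descriptive: the distribution of doses reached, the dose at first response with the count threshold stated, and tolerability by dose. Make no optimum-dose claim. Label any dose-response model exploratory, and require it to account for dose and count history.
2. **Objective 1.6, only if the full protocol does not already settle it.** State that a simple correlation of post-titration levels with response will not be interpreted as an exposure effect. Report as exploratory either the week-2 level drawn before any dose change, or a longitudinal model with lagged dose and prior count. Name the response definition.

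The cost is a narrower dose claim and some wording. If the week-2 option is chosen, a note on the order of sampling and dose change is also needed. Both analyses use blood counts and PK samples already in Table 3. Precision will be low with about 19 to 45 eltrombopag patients at full enrollment, and fewer if the trial stops early, which is a further reason for the exploratory label.

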5.1 Monitoring and Dose adjustment

5.1.1 Patients in the treatment group will be started at dose level 0 (table 1), the dose will be modified every 2 weeks based on the schema outlined in table 2 after a careful review of safety information at the previous dose level.

Table 1 Dose Level

Dose level	Eltrombopag dose

-1	25mg
0	50mg
1	75mg
2	125mg
3	150mg

Table 2 Dose Modification Schema

Platelet count X 10 ⁹ /l	Dose
< 50	Increase by 1 dose level
50-200	No change
201-400	Decrease by 1 dose level
> 400 at any time	Stop the drug

- 5.1.2 Drug will be stopped and patients will be taken off study if at any time platelet count is $\geq 400 \times 10^9/l$. This count will be carried forward to day 57 for analysis of primary endpoint and counted as success.
- 5.1.3 Patients of East Asian ancestry will start at dose level -1 and dose escalation will stop at dose level 2 (maximum dose 125 mgs).
- 5.1.4 The study drug will be stopped after 8 weeks and all patients will be monitored for additional 4 weeks after the last dose of study drug.
- 5.1.5 Patients will be taken off study: 1) at patient request, or 2) after completing 12 weeks.

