We will use a Bayesian adaptive algorithm (Berry, 1994) to randomize patients between the two treatment arms. The first 20 patients will be randomized fairly (i.e. fixed allocation of 1:1) between the two arms, after which the response adaptive randomization will begin. As the trial progresses and data accrue, the randomization will become unbalanced in favor of the treatment that, on average, has better results in terms of response, so that each successive patient is more likely to receive the treatment showing better results.

The randomization algorithm based upon this method will be implemented by using the Clinical Trial Conduct website developed by the Department of Biostatistics at M.D. Anderson Cancer Center.

The target enrollment for the study is a maximum of 64 patients, and we expect to enroll an average of 2 patients per month. We will follow all patients until they go off study. We assume a Beta(0.4, 1.6) prior distribution for the probability of response in each arm. We use the following notation: We denote the response rate in the placebo arm as R_p , and the response rate in the eltrombopag arm as R_E . We then denote P_p as the probability that the response rate in the placebo arm is greater than the response rate in the eltrombopag arm. Formally,

$$P_p = \text{Prob}(R_p > R_E \mid \text{data from patients evaluated at day 57}) \text{ and} \\ P_E = 1 - P_p = \text{Prob}(R_E > R_p \mid \text{data from patients evaluated at day 57})$$

The trial will be stopped early and eltrombopag (placebo) selected as being superior if at any time during the course of the trial $P_p > 0.98$ (< 0.02). If the trial is not stopped early and all 64 patients are enrolled and evaluated at day 57, then eltrombopag will be declared superior (inferior) if $P_p > 0.975$ (< 0.025).

After the first 20 patients are randomized fairly, patients will be randomized to the eltrombopag arm with probability $\max(0.20, P_p)$ and to the placebo arm with probability $\max(0.20, P_e)$. In other words, randomization probabilities are subject to the constraint that the minimum randomization probability to either arm is 20%.

The primary endpoint is development of a platelet count $\geq 30 \times 10^9/l$ at day 57 without platelet transfusion within 7 days. Patients who drop out of the trial before completion of day 57 with a platelet count $\geq 30 \times 10^9/l$ at the time of discontinuation will be considered successes with respect to the primary endpoint.

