Patients who drop out of the study after being randomized but before receiving any study drug will not be included in the analysis and will be replaced. All patients who receive a single dose of study drug will be included in the analysis.

Safety Monitoring

Patient safety will be monitored during this trial by reviewing the rate of development of toxicity, relapse, and mortality.

If a patient develops a grade 3 or higher toxicity attributed to the drug, the study drug will be stopped in that patient. This may be recommenced at the discretion of PI after resolution of the toxicity and review of the data.

For grade 4 toxicity, the PI will routinely review patient data and will temporarily halt the study pending study team review if a high rate of unexpected grade 4 toxicity is noticed. The case report form used for data collection will be PDMS/CORE.

We will use a formal Bayesian monitoring rule to monitor the rate of death or relapse on this study. We wish to ensure that the rate of death/relapse at day 57 is no more than 30% in either study arm. If there is a high probability that this rate is greater than 30% in either arm, we will temporarily halt and review the data with the MDACC IRB and FDA before continuing.

The method of Thall, Simon, and Estey will be employed separately in each arm to perform this monitoring. We will assume a noninformative Beta(0.6, 1.4) distribution on the prior probability that a patient experiences death or relapse, which has a mean of 30% but carries little prior information. We will start monitoring with the first patient in each arm and will use the following rule: halt accrual onto an arm if at any time during the course of the study:

$$\Pr\{57\text{-day death/relapse on the arm} > 30\% \mid \text{data from patients evaluable at day 57}\} > 0.925$$

In other words, if at any time during the trial, we determine that there is greater than a 92.5% chance that the 57-day death/relapse in an arm is greater than 30%, we will temporarily halt the arm pending IRB and FDA review.

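### Section 5.1.2 takes patients off study, not only off drug, at a platelet count of 400 or more; this conflicts with 5.1.4 and Table 2 and may cost follow-up in a probably small group

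*Combined protocol and SAP*

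**What the plan says.** Four places in the combined protocol and SAP bear on a patient whose count reaches 400 × 10⁹/l.

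- **5.1.2:** "Drug will be stopped and patients will be taken off study if at any time platelet count is" at or above 400. For the primary endpoint it adds: "This count will be carried forward to day 57 for analysis of primary endpoint and counted as success".
- **Table 2:** the row "> 400 at any time" stops the drug and says nothing about leaving the study. A count of exactly 400 falls in the row above it (201–400), which lowers the dose by one level.
- **5.1.4:** after the 8 weeks of treatment, "all patients will be monitored for additional 4 weeks after the last dose of study drug".
- **Statistical Considerations, Adaptive Randomization:** "We will follow all patients until they go off study".

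Table 3 schedules blood counts, toxicity and transfusion numbers every two weeks to week 12, and again on the date of the last dose. Weeks 10 and 12 are by telephone with local blood work. A marrow and an eye examination fall within 3 months of the last dose.

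**The concern.** Leaving the study is triggered here by an outcome, a high platelet count, at the moment the drug is withdrawn. Under the follow-up sentence in Statistical Considerations, scheduled observation then ends. Toxicity (objective 1.2), "Number of platelet and red cell transfusions" (1.3.2) and bleeding (1.3.3) are secondary objectives, and the off-drug weeks are part of the planned schedule for them. The Safety Monitoring rule also needs death or relapse status at day 57 in each arm.

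Staff cannot follow both 5.1.2 and the plain reading of 5.1.4 for the same patient. At a count of exactly 400 they cannot follow both 5.1.2 and Table 2. Which data exist for these patients would depend on which instruction was followed.

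**Working it through.** The plan gives no figure of its own on this point, so there is none to reproduce. The check counts what is lost under each of the two competing rules.

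**Inputs.** Assessments at weeks 2, 4, 6, 8, 10 and 12 (Table 3), which is 84 planned days. Post-drug monitoring of 4 weeks, or 28 days (5.1.4). Maximum enrollment of 64 (Adaptive Randomization). Assumptions: the stop falls on a scheduled visit; day 57 is the end of week 8; 32 patients are on eltrombopag (equal allocation); 2% to 10% of them reach 400. The documents give no such rate.

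**Loss per affected patient.** If 5.1.2 governs, a stop at week *w* loses every visit after *w*, and 7*w* days are observed. If 5.1.4 governs, it loses every visit after *w* + 4, and 7*w* + 28 days are observed.

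| Stop at week | Visits lost, 5.1.2 | Days observed of 84 | Visits lost, 5.1.4 | Days observed of 84 |
|---|---|---|---|---|
| 2 | 5 (weeks 4–12) | 14 (17%) | 3 (weeks 8–12) | 42 (50%) |
| 4 | 4 (weeks 6–12) | 28 (33%) | 2 (weeks 10, 12) | 56 (67%) |
| 6 | 3 (weeks 8–12) | 42 (50%) | 1 (week 12) | 70 (83%) |
| 8 | 2 (weeks 10, 12) | 56 (67%) | 0 | 84 (100%) |

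**Day 57.** Under 5.1.2, any stop before week 8 leaves day 57 unobserved. Under 5.1.4, a week-2 stop is watched to week 6 (day 42) and still misses it. A week-4 stop is watched to day 56, which is within the 3-day window that Table 3 allows. The post-study marrow assesses disease status but need not fall on day 57.

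**Number affected.** 32 × 0.02 = 0.64 and 32 × 0.10 = 3.2 patients. The chance of at least one is 1 − 0.98³² = 48% to 1 − 0.90³² = 97%. If adaptive allocation favoured eltrombopag as far as the 20% floor allows, the arm would have about 10 + 0.8 × 44 = 45 patients, and 0.9 to 4.5 would be affected.

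**Arm-level loss of planned patient-days,** rate × (1 − days observed/84), at 2% to 10%:

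- 5.1.2 governs: 1.7% to 8.3% if all stop at week 2, and 0.7% to 3.3% if all stop at week 8.
- 5.1.4 governs: 1.0% to 5.0% if all stop at week 2, and none if all stop at week 8.

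**What the fix requires.** Assessments through week 8 and for at least 4 weeks after the last dose are weeks {4, 6, 8}, {6, 8}, {8, 10} and {10, 12} for stops at weeks 2, 4, 6 and 8. That is 3, 2, 2 and 2 visits more than 5.1.2 gives, and 1, 0, 0 and 0 more than 5.1.4 gives.

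**The case against.** The strongest reply is that 5.1.4 says all patients, so the monitoring is already there and the defect is one of wording. Much of this stands. If 5.1.4 governs, the fix adds one visit, at week 8, for a week-2 stop, and nothing for later stops. It is therefore wrong to say that the data are lost; they could be lost, depending on which rule is followed. What remains is that nothing in the text says which rule prevails, and that even under 5.1.4 a week-2 stop is not seen at day 57.

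The second reply is size. Entry requires a count of 20 or below, or transfusion dependence, and Table 2 lowers the dose from 201 upward, so few patients should reach 400. This also stands, and it is why the point is minor.

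Several stronger readings are tempting, and the documents do not support them.

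- A reader might infer that shorter follow-up flatters eltrombopag on transfusions. This needs the affected patients to be mainly on that arm, transfusions to recur off drug, and an analysis that ignores follow-up time. The first two are not stated. The third cannot be judged, because the analysis details are deferred to a fuller protocol text not supplied here.
- A reader might see a contradiction with 5.1.5: "Patients will be taken off study: 1) at patient request, or 2) after completing 12 weeks". That list is not said to be exhaustive, and 5.1.2 can stand as an additional reason.
- A reader might contrast drug-attributed toxicity of grade 3 or higher, where "the study drug will be stopped in that patient. This may be recommenced at the discretion of PI after resolution of the toxicity". That is a different trigger, and there is no inconsistency.

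**Conclusion.** The point holds as a minor one. Followed as written, 5.1.2 together with the follow-up sentence ends observation of secondary and safety outcomes because of an outcome, and it conflicts with 5.1.4 and with Table 2. Per affected patient the loss is 5, 4, 3 or 2 of six assessments if 5.1.2 governs and 3, 2, 1 or 0 if 5.1.4 does. The last-dose assessment and the marrow and eye examinations are tied to the last dose and may still be done. At arm level the loss is probably small, but this rests on the assumed 2–10% rate and on 32 patients in the arm.

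Day-57 death or relapse status could be missing for some of these patients. The safety rule uses patients evaluable at day 57; the text supplied does not define the term, so how they would be handled is not known.

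A reader might also infer that the primary result is at risk. It is not. The wording varies between reaching the count by day 57 and having it at day 57, but the carry-forward in 5.1.2 is explicit and settles these patients as successes either way.

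**What to change.** - In 5.1.2, replace the off-study instruction with: study drug stopped; patient remains on study. Specify Table 3 assessments through day 57 and for at least 4 weeks after the last dose, including death and relapse status at day 57.
- Use one threshold: in Table 2 make the decrease row 201–399 and stop the drug at 400 or above, matching 5.1.2.
- Keep the carried-forward success as the primary analysis. A sensitivity analysis using the observed day-57 count and transfusion status would be optional.

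The cost is an amendment and, compared with 5.1.2 as written, three assessments for a week-2 stop or two for a stop at week 4, 6 or 8. All are already in Table 3. Those at week 10 or 12 are by telephone with local blood work; those at weeks 4 to 8 are clinic visits for a patient no longer on drug, which is the real burden. Visits beyond this window, such as weeks 10 and 12 after a week-2 stop, are not recovered; the fix does not ask for them.
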